## 7. Research question and objectives

### 7.1 Research question

The research question prompting this study is the decisional process that assigns subjects with previous VTE who concluded the maintenance anticoagulation, to one of the alternative options: extended anticoagulation, alternative pharmacological prophylaxis, or interruption of the pharmacological prophylaxis. The secondary research question is the estimation of the true rate of events during prolonged observation under true-to-life conditions, among subjects allocated to extended anticoagulation or to alternative prophylaxis or to no pharmacological prophylaxis.

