#### 8.1.2 Secondary endpoints

The secondary endpoints include:

- the distribution of the reasons that were considered relevant by the attending physician to take the decision indicated as primary endpoint;
- the rate of thromboembolic complications and the combined rate of bleeding requiring at least an interview with the attending physician (major or clinically relevant non-major bleeding), or death from any cause during the 2-year follow-up.

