## **3. Unplanned follow-up visit**

Upon request of the subject, or by decision of the investigator based on the communications with the subject, there may be the need for unplanned follow-up interviews. This will usually occur when a thromboembolic complication or a bleeding complication or other events occurred, that make clinically relevant for the well-being of the subject a direct contact with the investigator.

The information to be collected at these visits is the same as that of the follow-up visit. Usually, these visits imply the conclusion of the follow-up on the individual subject.

The follow-up is to be concluded, filling the end-of-study form discussed below, when:

- a. a thromboembolic complication occurred;
- b. a major bleeding complication occurred. Clinically relevant non-major bleedings as well as minor bleedings do not automatically imply the interruption of the follow-up and the relevant decision will be taken by the investigator case by case on the best subject's interest;
- c. there was a substantial change in anti-thrombotic therapy, such as:
  - institution, by the investigator or another physician, of a prophylactic therapy in a subject for whom the decision was taken not to continue the pharmacological prophylaxis;
  - replacement, by the investigator or another physician, of the current therapy with a new therapy of another therapeutic class. Changes of dosage of the same therapy do not imply interruption of the follow-up;
  - interruption, by the investigator or another physician or by subject's spontaneous decision, of the prescribed prophylactic treatment;
- d. an event occurred, that implied the impossibility to continue a correct monitoring, e.g., a planned/unplanned intervention requiring prolonged anticoagulation (e.g., surgery or immobilization).

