#### **10.4.4 Other endpoints**

Other monitored endpoints include the occurrence of hospitalization and the change of prophylactic therapy, including:

- institution – by the attending physician or other physician - of a therapy in subjects who stopped any prophylactic treatment at recruitment;
- change – by the attending physician or other physician - of the prophylactic treatment assigned at recruitment, and
- interruption – by the attending physician, other physician or by spontaneous subject's decision - of the prophylactic treatment assigned at recruitment.

Hospitalizations do not necessarily imply interruption of the follow-up, unless associated to a primary endpoint (thromboembolic event, bleeding, death) or result in the impossibility to continue an appropriate monitoring (e.g. need for anticoagulation). Consequently, hospitalizations can be analyzed by chi square across sub-populations as proportion of subjects with event or, in case of an appreciable number of events, by Poisson regression.

Any change in therapy, instead, implies interruption of the follow-up. Changes in therapy will be tabulated, stratified by sub-population, as absolute number and proportion and, if appropriate, analyzed by chi square and/or by logistic regression.

In addition, the reasons for study termination may be considered an endpoint. These will be tabulated by sub-population and compared, if appropriate, by chi square or ordinal logistic regression. If required by the Steering Committee, unplanned *post-hoc* subgroup analyses may also be performed.

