#### **11.1 Steering Committee**

The study will be guided and monitored by a Steering Committee. The members of the Steering Committee are listed in § 3.1 above.

The Steering Committee has the responsibility of:

- a. supervising the progress of the study and ensuring that the protocol is carefully followed by every participant. To exert this responsibility the Steering Committee may appoint Monitors and, in such a case, is informed of all monitoring activities and, in particular, of the reports of the Data Monitoring and Safety Board (§ 3.2.3).
- b. proposing Protocol Amendments to solve, clarify and implement possible doubts, questions, or practical difficulties that may arise during the study, or that may become necessary owing to the scientific progress in the specific therapeutic field, to ensure that the scientific validity of the study is maintained.

- c. resolve doubts as to the classification of outcomes, if the need arises. To this aim, the individual subject's data supplied to the Committee will be anonymous as to the subject and to the Center, and blinded as to the applied treatment, if any.
- d. resolve doubts as to the protocol violation, if any, deciding whether the possible violation is to be considered a minor deviation, a major deviation, or a true violation, and whether the case has to be included into the ITT dataset (no other dataset is planned in this study). To this aim, the individual subject's data supplied to the Committee will be anonymous as to the subject and to the Center, and blinded as to the applied treatment.
- e. participate in the Writing Committee.

The Steering Committee appointed a Core Team of five persons, including a statistician. The Core Team has the responsibility of:

- a. managing the study according to the needs that may arise, and reports to the whole Steering Committee as needed;
- b. presenting to the Steering Committee a yearly report on the status of the trial, including the clinical results that may arise, until the closure of the study, which will incorporate the conclusions of the DMSB evaluation. The term "yearly" should be intended as the time at which the data relevant to the end-of-observation-year visit on the last subject recruited have been recorded and validated. Consequently, there will be one interim report; the second report coincides with the final study report.

The components of the Core Team are listed in § 3.1 above.

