#### Reason for concluding the follow-up of this patient

The patient reached the end of the planned observation period	 date:  _ _ / _ _ / _ _ _ _ _
	0-no; 1-yes; default=no exact date: dd/mm/yyyy
Showed a thromboembolic event	 date:  _ _ / _ _ / _ _ _ _ _
Showed a major bleeding event	 date:  _ _ / _ _ / _ _ _ _ _
Had a major change in therapy	 date:  _ _ _ _ _ / _ _ _ _ _
Reported another event preventing continuation of the follow-up	 date:  _ _ _ _ _ / _ _ _ _ _
	these dates may be incomplete (no day)
The patient died	 date:  _ _ / _ _ / _ _ _ _ _
The patient reported to another hospital	 date:  _ _ _ _ _ / _ _ _ _ _
The patient moved to another place	 date:  _ _ _ _ _ / _ _ _ _ _
The patient was lost to follow-up	 date:  _ _ _ _ _ / _ _ _ _ _

**CHECK:** at least one must be marked yes; if thromboembolic event is marked, there must be a thromboembolic event in the last follow-up form; if bleeding event is marked, there must be a bleeding event in the last follow-up form, items 1-9; if died is marked, there should be death=yes in last follow-up form, if other event is marked, there must be a "other event" marked in the last follow-up form.

After this form is concluded, the case is closed and cannot be modified by the users. It can be re-opened upon request (ticket), endorsed by the study supervisors.

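### Deaths, bleeds and recurrences after a subject's record is closed are not systematically collected, so 2-year all-cause death and event rates by baseline decision are incomplete and open to informative censoring

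*Combined protocol and SAP*

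**What the plan says.** **What is to be estimated.** Section 7.1 sets as its secondary question "the estimation of the true rate of events during prolonged observation under true-to-life conditions" among subjects allocated to each of the three options. Section 8.1.2 asks for the thromboembolic rate and for the combined rate of major or clinically relevant non-major bleeding, "or death from any cause during the 2-year follow-up". Section 8.1 stratifies these by the sub-population that the baseline decision creates. Section 11.1 has the Steering Committee decide, for protocol violations, "whether the case has to be included into the ITT dataset (no other dataset is planned in this study".

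**What is collected.** Section 8.3.1, item 3, says "The follow-up is to be concluded, filling the end-of-study form discussed below, when" and then lists a thromboembolic complication, a major bleed, a substantial change in antithrombotic therapy, and an event that makes proper monitoring impossible. The example given for the last is "a planned/unplanned intervention requiring prolonged anticoagulation (e.g., surgery or immobilization". Item 4, the synopsis (End-of-study visit) and section 10.4.4 carry the same idea. In Appendix IV the follow-up form sends thrombotic complications, deaths, preventing events and new, discontinued or replaced therapy to the end-of-trial form. The Interview ID check rejects a follow-up form once the conclusion form exists. The end-of-study form adds: "After this form is concluded, the case is closed and cannot be modified by the users", although supervisors may endorse a request to reopen. No section plans a check of vital status or events after closure.

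**How it is analysed.** Section 10.4.3 reports proportions from whatever observations are available, and allows chi-square and/or survival analysis. It does not say how closure is to be handled.

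**The triggers are not uniform.** Section 8.3.1 closes at a major bleed, while the follow-up form leaves any bleeding to the investigator. Section 8.3.1 says "Changes of dosage of the same therapy do not imply interruption of the follow-up"; section 10.4.4 says "Any change in therapy, instead, implies interruption of the follow-up". Section 8.3.1 closes at replacement by another class, while the follow-up form closes at any replacement. These passages must be reconciled.

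**The concern.** Apart from month 24, withdrawal, relocation and plain loss to follow-up, subjects leave observation because of an outcome, a change of management or a rise in risk. Two kinds of information go missing.

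- After a thromboembolic event, later bleeding and death are not looked for, so one secondary endpoint is cut short by the other.
- After a change of management, later recurrences, bleeds and deaths are not looked for, so the rates describe subjects only while they stay on the option chosen at baseline.

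The triggers also differ by group. Extended anticoagulation and alternative prophylaxis can close through interruption or replacement, whereas the untreated group closes through the start of a therapy. There is no reason to expect equal closure rates, so a comparison of crude proportions can show a difference that closure alone has produced. The DMSB would judge continuation on the same incomplete data.

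The trigger is also wide in practice. The follow-up form counts superficial vein thrombosis and transient ischemic attack as thrombotic complications, so either would end the observation of mortality.

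**Working it through.** **Step 1. The plan's own figure (section 10.2).** With N = 3,200, Cohen's w = 0.055 and 2 degrees of freedom, the noncentrality is 3,200 × 0.055² = 9.68. Noncentral chi-square power is 0.802 at alpha 0.05 and 0.797 at 0.048, so the stated 80% reproduces. The detectable deviations also reproduce as w × √p: 0.055 × √0.05 = 0.0123 and 0.055 × √0.01 = 0.0055. Section 10.2 assumes that nearly all recruits are followed for a year or more, and gives no rate of therapy change.

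**Step 2. Subjects and person-time lost.**
- From section 10.2: thromboembolism 0.05 per year; bleeding or death 0.01 per year.
- Assumed: a constant hazard c per year of closure by therapy change or another event, from 0 to 0.30.
- Simplification: every bleed or death ends observation, although a non-major bleed need not.

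With L = 0.05 + 0.01 + c:
- observation ended before year t: 1 − exp(−Lt)
- share of 2-year person-time lost: 1 − [1 − exp(−2L)]/(2L)
- crude 2-year recurrence proportion, all subjects of the group in the denominator: 0.05 × [1 − exp(−2L)]/L
- reference without other closure: 1 − exp(−0.10) = 9.5%

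| c per year | ended before 1 year | ended before 2 years | person-time lost | crude recurrence |
|---|---|---|---|---|
| 0 | 5.8% | 11.3% | 5.8% | 9.4% |
| 0.05 | 10.4% | 19.7% | 10.2% | 9.0% |
| 0.10 | 14.8% | 27.4% | 14.4% | 8.6% |
| 0.20 | 22.9% | 40.5% | 22.0% | 7.8% |
| 0.30 | 30.2% | 51.3% | 28.7% | 7.1% |

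Two groups with the same true rate:
- c = 0.05: 0.05 × (1 − e^−0.22)/0.11 = 9.0%
- c = 0.30: 0.05 × (1 − e^−0.72)/0.36 = 7.1%

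The gap comes from closure alone. The person-time rate stays at 5.0 per 100 in both groups, provided closure is unrelated to risk.

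**Step 3. Deaths.** All inputs except the 0.05 recurrence rate are assumptions: death 0.005 per year while the record is open, major bleeding 0.005 per year, and death k times as frequent after closure.

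With h = 0.05 + 0.005 + c, captured deaths over 2 years are 0.005 × [1 − exp(−2(h + 0.005))]/(h + 0.005). Missed deaths are the integral over 2 years of 0.005k × C(t), where C(t) is the fraction closed and alive: C(t) = h[exp(−0.005kt) − exp(−(h + 0.005)t)]/(h + 0.005 − 0.005k).

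| c | k | true 2-year deaths | captured | share missed |
|---|---|---|---|---|
| 0 | 1 | 1.00% | 0.94% | 5% |
| 0.1 | 1 | 1.00% | 0.86% | 14% |
| 0.1 | 2 | 1.13% | 0.86% | 25% |
| 0.2 | 2 | 1.21% | 0.78% | 36% |
| 0.2 | 5 | 1.84% | 0.78% | 58% |

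Kaplan-Meier with closure as censoring gives 1 − exp(−0.01) = 1.0% in every row. That is right when k = 1 and too low when k exceeds 1. Because no deaths are sought after closure, the study's data cannot show which case applies.

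**The case against.** A reader might infer that 2-year outcomes cannot be measured at all and that records are shut for good. The documents do not support that.

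- First thromboembolic events, and bleeds and deaths before closure, are recorded. Section 10.4.3 permits survival analysis, so first event on the initial management is estimable.
- A closed case can be reopened on request. This is ad hoc, however, and not a planned check on every subject.
- A pulmonary embolism followed by death is not always counted as thromboembolism only. The follow-up form covers everything since the last contact, and the end-of-study form has separate dates for each outcome. If both are learned of at one contact, both are captured. The loss arises when the embolism prompts an unplanned visit that closes the record first.
- Surgery or immobilization does not close a case by itself. It does so only where it needs prolonged anticoagulation and prevents proper monitoring.
- Nor can one say that the group with most recurrences suffers most. Under the hazards above, therapy change can outweigh recurrence as a cause of closure.

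The sponsor could add that section 10.3 defines the population as everyone monitored, that the ITT term in section 11.1 concerns protocol violators, and that the analyses are exploratory. It is fair that the intended estimand is partly inferred. But section 7.1 asks about subjects by allocated option under real-life conditions, and section 8.1.2 sets a 2-year horizon for death from any cause. Neither is limited to time on the initial management.

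**Conclusion.** The point holds in this form: outcomes after closure are not systematically collected, so 2-year all-cause death and event rates by baseline decision are incomplete and open to informative censoring. Crude proportions with all subjects in the denominator are biased low, by an amount that depends on each group's closure rate. Person-time or survival methods repair this only if closure is unrelated to later risk. That is doubtful for closure triggered by events, and untestable here.

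Over the assumptions shown, crude recurrence falls from 9.5% to between 9.4% and 7.1%, and 5% to 58% of 2-year deaths are missed. Closure rates, the split of bleeding and death, and mortality after closure are assumptions, so these figures show a range and do not predict a value. The primary endpoint is measured at the baseline visit and is untouched.

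**What to change.** **Preferred.** In section 8.3.1 (items 3 and 4), section 10.4.4, the synopsis and Appendix IV (the Interview ID check and the end-of-trial decision boxes), record the event or change with its date and keep collecting. As a minimum, obtain vital status, thromboembolic events and bleeding at the routine month-12 and month-24 contacts for all subjects. End data collection only at death, withdrawal of consent, loss to follow-up or month 24. Adapt the end-of-study checks that require the event to be in the last follow-up form. This changes data collection only, not treatment.

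In section 10.4.3, make the main analysis by baseline decision over all observed time. Use person-time or cumulative-incidence methods in place of crude proportions, with death as a competing event for thromboembolism. Keep the analysis censored at change of management as secondary. That analysis needs one definition of change, so the conflicting passages on dose change, same-class replacement and bleeding must be reconciled.

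**Alternative.** If collection after closure is not adopted, restate the secondary objective and endpoint as first event while on the initial management, with competing-risk analysis. Drop the wording on 2-year all-cause death and ITT.

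**Cost.** The preferred fix needs extra contact forms and a protocol and e-CRF amendment, with ethics submissions in nine countries. Sections 8.3.1 and 8.2.2 already describe the contacts as routine and require a permanent contact. Section 8.3.1 has consent cover calls and annual visits during follow-up. Whether it extends past closure cannot be checked in this copy, so a consent amendment may be needed.

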	
Unplanned follow-up visits
 
It is possible, as usual during long-term monitoring of subjects, that visits are needed at the center upon request by the subject or based on the physician's decision. These unplanned visits, which will typically correspond to an event of recurrence or of bleeding, will record the same information as a standard follow-up visit. Performing an unplanned visit is not by itself considered a reason for terminating the study, unless the visit corresponds to one of the study endpoints (thromboembolic complications, bleeding complications, or other events preventing continuation of the follow-up).
 
End-of-study visit
 
The end-of-study information, collected at the last planned or unplanned contact with the subject, will only include the reason for terminating the observation on the individual subject.
 
The end-of-study visit will have to be completed for all subjects entered into the follow-up, and may occur:
 
 
at the end of the planned follow-up period;
 
when the investigator detects, or is informed of, the occurrence of a secondary endpoint (new thromboembolic event, major bleeding, clinically relevant non-major bleeding requiring a change of treatment; subject's death);
 
change (with the exception of dosage) or interruption of the prophylactic treatment assigned at recruitment (including not pharmacological treatment) by the attending physician or other physician;
 
subject's decision to stop the prescribed prophylaxis;
 
events occurred, which prevented the continuation of the follow-up (subjects lost to follow-up for any reason, including reporting to another center).
 

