## DECISION: in case of

- a) thrombotic complication;
- b) death
- c) event preventing continuation
- d) newly instituted therapy
- e) discontinued therapy
- f) change to new therapy

go to END-OF-TRIAL.

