## IN CASE OF:

- a) bleeding complication
- b) hospitalization, ASK if patient remains on trial or goes to END-OF-TRIAL.

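### The texts conflict on whether a switch to another drug of the same class ends follow-up, and the CRF template applies the broader rule

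*Combined protocol and SAP*

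**What the plan says.** **Drug changes.** Four places state when a change of therapy ends observation.

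- Section 8.3.1, item 3 (Unplanned follow-up visit) lists examples of a substantial change. For a change of drug, the example is replacement "of the current therapy with a new therapy of another therapeutic class". Dosage is exempt: "Changes of dosage of the same therapy do not imply interruption of the follow-up".
- The synopsis (End-of-study visit) ends follow-up on "change (with the exception of dosage) or interruption of the prophylactic treatment assigned at recruitment". It exempts dosage but has no class test.
- Section 10.4.4 states: "Any change in therapy, instead, implies interruption of the follow-up". It names no exception.
- The DECISION list of the follow-up form (Appendix IV) sends "change to new therapy" to the end-of-trial form, also with no class test.

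The end-of-study form then records a major change of therapy without defining major. After it is completed, users cannot modify the case, and re-opening needs an endorsed request. The follow-up form is not accepted once a conclusion exists.

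**Bleeding.** Section 8.3.1 ends follow-up when "a major bleeding complication occurred". The synopsis and the end-of-study item of 8.3.1 agree. The DECISION list omits major bleeding. The next block covers any bleeding complication and instructs the system to "ASK if patient remains on trial or goes to END-OF-TRIAL". For minor bleeding, section 8.3.1 leaves the decision to the investigator, whereas section 10.4.3 says it is not a reason to stop.

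**The concern.** A subject who moves from one drug to another of the same class has an end date that depends on the text applied. Section 8.1 defines the extended-anticoagulation sub-population to include another substance of the same class, so such a subject still fits that stratum when the CRF routing stops observation.

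The loss is one-sided. A subject without prophylaxis cannot switch within a class, and all the texts already end follow-up when therapy is started in such a subject. If switches follow bleeding or a perceived change in risk, the censoring is informative. Even if they do not, section 10.4.3 reports event rates as proportions by sub-population, and a shorter observation time in the treated strata lowers a crude proportion. Section 10.4.3 gives no rule for these terminations. The loss is also hard to repair: extra follow-up can be censored later at a recorded date, but events after closure are normally never collected.

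**Working it through.** **1. The texts side by side**

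| Event | 8.3.1 | Synopsis | 10.4.4 | CRF routing |
|---|---|---|---|---|
| Replacement, another class | ends | ends | ends | ends |
| Replacement, same class | not listed; continuation implied | ends | ends | ends |
| Dose change | continues | continues | not exempted in words | not in the end-of-trial list |
| Major bleeding | ends | ends | not addressed as a rule | site is asked |

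Class is not used consistently. Section 6.2 speaks of the same or another anticoagulant class and names NOACs, VKAs and LMWHs, so these are separate classes there. Section 8.1 describes extended anticoagulation as the same or another substance of the same class. Whether a VKA-to-NOAC switch is a same-class or a cross-class change depends on which usage applies.

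**2. The plan's own figure**

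Section 10.2 claims 80% power at Cohen's effect 0.055 with about 3,200 subjects, assuming almost all are monitored for at least one year. Noncentrality = 3,200 × 0.055² = 9.68. With 2 degrees of freedom and alpha 0.05, power is 0.802 (0.797 at alpha 0.048). The figure reproduces and is not in dispute. It matters here because it rests on observation time, which the end-of-follow-up rule controls.

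**3. Person-time lost in treated subjects**

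The documents give no switch rate. Assume a constant within-class switch hazard h of 0.05, 0.10 or 0.20 per person-year over two years.

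(a) Nothing else ends follow-up. Share lost = 1 − (1 − e^(−2h))/(2h). For h = 0.10: 1 − (1 − e^(−0.20))/0.20 = 1 − 0.906 = 9.4%. The other two values are 4.8% and 17.6%.

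(b) Other terminations occur at 16 per 100 person-years: 5 + 1 for the endpoints (section 10.2) plus an assumed 10 for undisputed therapy changes. Person-years per subject = (1 − e^(−2k))/k, with k = 0.16 + h.

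| h | Person-years | Lost | Still followed at 1 year, e^(−k) | Two-year crude recurrence, 0.05 × person-years |
|---|---|---|---|---|
| 0 | 1.712 | – | 85% | 8.6% |
| 0.05 | 1.633 | 4.6% | 81% | 8.2% |
| 0.10 | 1.560 | 8.9% | 77% | 7.8% |
| 0.20 | 1.426 | 16.7% | 70% | 7.1% |

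The last column shows a crude proportion falling while the true recurrence rate stays at 5 per 100 person-years. A person-time rate or a survival analysis would not shift for that reason alone. It would be biased only if switching is related to risk, which the documents do not quantify. In the no-prophylaxis group the disputed rule removes nothing.

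**The case against.** The list in 8.3.1 is introduced as examples, so it never states that a within-class switch continues. That is correct, and it is why continuation is described here as implied. It does not remove the problem, because naming another class has no purpose if any new drug ends follow-up.

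A reader might draw four stronger conclusions that the documents do not support.

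- *That a dose change ends follow-up under 10.4.4.* The sentence follows a list of institution, change and interruption that does not name dosage. The synopsis and 8.3.1 both exempt dosage, and the follow-up form codes dose changes separately without routing them to the end of trial. This is loose wording, not a rival rule.
- *That major bleeding has two competing rules.* The synopsis, 8.3.1 and the end-of-study form treat it consistently as a reason to stop. The prompt is generic and does not say a major bleed may continue. The routing fails to enforce the text. Bleeding grade is recorded, so time observed after a major bleed could be censored at analysis.
- *That drug-switch handling will differ by centre.* The database is single and central (section 8.4), so the likelier result is one uniform rule that differs from 8.3.1. Site discretion remains for bleeding and hospitalization.
- *That rates across sub-populations are made non-comparable.* This is not shown. Undisputed stops and cross-class switches already censor by stratum, the strata are chosen by physicians, and section 10.1 calls the analyses exploratory. Reconciling the wording leaves those limits in place.

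**Conclusion.** The conflict over within-class drug switches stands. Section 8.3.1 implies that observation continues. The synopsis, section 10.4.4 and the CRF template end it, and the template then blocks further follow-up forms unless the case is re-opened. The stratified secondary event rates can be affected. The primary endpoint is fixed at baseline and is not.

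The size cannot be determined from the documents. On assumed constant hazards of 5, 10 or 20 per 100 person-years, the broader rule removes about 4.8%, 9.4% or 17.6% of two-year person-time in treated subjects if nothing else ends follow-up. With an assumed 16 per 100 person-years of other terminations, the losses are about 4.6%, 8.9% or 16.7%. The first set is measured against a full two years, so it should not be read as the loss relative to 8.3.1, which already ends follow-up for other reasons. Whether the censoring is informative is plausible but not established.

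Two lesser points also stand: the routing does not enforce the protocol text on major bleeding, and 8.3.1 and 10.4.3 differ on minor bleeding. The correction is worth making, and no view is taken on which rule is right.

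**What to change.** 1. Reconcile the synopsis, 8.3.1, 10.4.3, 10.4.4 and the Appendix IV follow-up and end-of-study forms to one observation-ending rule. Define class, define major change on the end-of-study form, and carry the existing dosage exception into 10.4.4.
2. Program the e-CRF to match, including its routing for major bleeding, and align the wording on minor bleeding.
3. Until this is done, do not let the e-CRF close a case automatically for a within-class drug switch. Keep recording the routine contacts, with the type and date of the change.
4. Report the secondary event rates twice: censored at the switch, and over all observed time.

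The cost is protocol wording submitted to the ethics committees of the participating centres in nine countries, an e-CRF branching change with a date field, and one additional analysis. The follow-up form already captures the type of change and the replacement drug. The calls and annual visits are described as routine, and the consent in 8.3.1 covers them.
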